5 STUDY PLAN, PROCEDURES, AND ASSESSMENTS

5.1 Description of Study Visits

The mortality, clinical effects, safety, and tolerability of treatment will be evaluated from baseline through Day 60. Evaluations at screening and during the 5-day treatment occur in person. Evaluations after the 5-day treatment to the end of the study (days 6 to 60) will typically occur via telephone. The Schedule of Assessments is shown in [Section 1.2](#).

5.1.1 Screening (-3 Days to Day 0)

The following procedures will be performed at Screening:

- Evaluate all inclusion and exclusion criteria to ensure that patients meet all inclusion criteria and none of the exclusion criteria.
- Medical history, pre-existing conditions, and comorbidities. Include the symptom onset date for COVID-19 symptoms and date of COVID-19 test.
- Diphenhydramine, hydroxychloroquine, and azithromycin all prolong the cardiac QT interval, increasing risk of fatal cardiac arrhythmia. Therefore, severely-ill subjects receiving multiple drugs that prolong QT intervals will be reviewed carefully by the P.I. on a case-by-case adjudication for benefit-risk ratio and close cardiovascular monitoring. Note, subjects who have baseline QT prolongation are excluded from this study.
- Obtain informed consent before the starting any study specific procedures, including COVID testing.

5.1.2 Baseline (Day 0)

The following procedures will be performed at Baseline (first assessment prior to treatment):

- Confirm eligibility (review inclusion/exclusion criteria).
- Randomize patient to study arm.
- Demographics (age, sex, race, height and weight)
- Concomitant medications/therapies
- Vital signs: heart rate, systolic and diastolic BP, body temperature, respiratory rate
- SpO₂ and supplementation oxygen mode/flow rate
- ECG monitoring (telemetry) or 12-lead ECG: record aberrant changes in waves/ intervals
- Hematology, biochemistry tests
- Cytokine and chemokine assays
- Ordinal scale and NEWS2 assessments
- AEs

5.1.3 Treatment Period (Day 1 to Day 5)

The following procedures will be performed during the Treatment Period (Day 1 to Day 5):

- Administer Ampion or placebo as a daily IV infusion. Begin treatment within 6 hours of randomization.
- Concomitant medications/therapies

- Vital signs: heart rate, systolic and diastolic BP, body temperature, respiratory rate – vital signs are collected shortly after (within 30 minutes) treatment.
- SpO2 and supplementation oxygen mode/flow rate
- ECG monitoring (telemetry) or 12-lead ECG: record aberrant changes in waves/ intervals – monitored as needed for patients who have abnormal readings or events requiring measurements.
- Hematology, biochemistry tests – these tests are performed at baseline and every other day through treatment and through hospital stay unless an abnormal value is observed. In the case of an abnormal lab result, continue to collect and test those samples to follow subject through resolution.
- Cytokine and chemokine assays – these tests are performed at baseline and at Day 5.
- Ordinal and NEWS2 assessments
- AEs

5.1.4 Hospitalization Period, as applicable (Day 6 through Day 7)

Hospitalization refers to hospital and/or in-patient settings. The following procedures will be performed for the remainder of the hospitalization, as applicable:

- Concomitant medications/therapies
- Vital signs: heart rate, systolic and diastolic BP, body temperature, respiratory rate
- SpO2 and supplementation oxygen mode/flow rate
- ECG monitoring (telemetry) or 12-lead ECG: record aberrant changes in waves/ intervals – monitored as needed for patients who have abnormal readings or events requiring measurements.
- Hematology, biochemistry tests – these tests are performed at baseline and every other day through treatment and through hospital stay unless an abnormal value is observed. In the case of an abnormal lab result, continue to collect and test those samples to follow subject through resolution.
- Cytokine and chemokine assays – these tests are performed at hospital discharge.
- Ordinal scale and NEWS2 assessments
- AEs

5.1.5 Post-Treatment Follow-Up (Days 28, 60)

The following procedures will be performed at all follow-up visits (Days 28, 60):

- Mortality
- Concomitant medications/therapies
- Hospital LOS
- ICU LOS
- Ordinal scale and NEWS2 assessments
- AEs

5.2 Assessment Methods

Demographic Data

Demographic data will be collected from medical records: age, gender, race, height and weight, comorbidities.

Medical History

Medical history and pre-existing conditions will be collected from medical records.

Concomitant Medications

Concomitant medications will be collected from the medical records: prior (pre-hospitalization) concomitant medications, in-patient concomitant medications.

Mortality

All-cause mortality will be recorded at hospital discharge, Days 28 and 60, as applicable. Cause of mortality will be assessed and documented. All-cause mortality is calculated for the primary endpoint as the percentage of participants with a successful outcome (life) or unsuccessful outcome (death).

Length of Stay (LOS)

Due to the COVID-19 health emergency, the Centers for Medicare and Medicaid is temporarily allowing long-term care facilities not normally used as a resident's room to accommodate beds and residents for care in emergencies/situations needed to help with surge capacity. Therefore, hospitalization refers to hospital and/or inpatient care during the COVID-19 health emergency. Inpatient care may include hospitals treating COVID-19 patients; dedicated COVID-19 treatment facilities with 24/7 care; and/or dedicated research facilities with 24/7 care.

Dates of hospitalization and ICU admission as well as discharge dates will be recorded at hospital discharge, Days 28 and 60, as applicable. The hospital LOS and ICU LOS will be calculated as follows:

- ICU admission: defined (in days) as the first study day when ICU status is changed to “yes” minus baseline date + 1
- Hospital LOS: is defined (in days) as the date of hospital discharge minus date of hospital admission + 1
- ICU LOS: defined (in days) as the date moved out of ICU minus first study date when ICU admission changed to “yes” + 1

Oxygen Use

Oxygen use measured as blood oxygen saturation (SpO2) and oxygen flow rate (liters per minute, lpm) will be recorded at every visit from baseline to Day 5.

Intubation/Extubation

Date and time of intubation/extubation and days on ventilator will be recorded at hospital discharge, Days 28 and 60, as applicable. Proportion of participants who progress to respiratory failure (i.e., need for mechanical ventilation, ECMO, non-invasive ventilation, or high-flow nasal cannula oxygen) will be evaluated.

Vital Signs

Vital signs will be collected daily during the treatment period and at follow-up visits from medical records as follows: heart rate (or pulse rate), systolic BP, diastolic BP, body temperature (°F in the US, °C out of the US), respiratory rate. Vital signs are collected shortly after (within 30 minutes) treatment.

Hematology

Hematology lab tests will be collected from the medical records at baseline and every other day through treatment and hospital stay (as applicable) unless an abnormal value is observed. In the case of an abnormal lab result, continue to collect and test those samples to follow subject through resolution.

The following hematology labs are tested: white cell count, red blood cell count, hemoglobin, hematocrit, mean cell volume (MCV), mean cell hemoglobin (MCH), mean cell hemoglobin concentration (MCHC), platelets, neutrophils, lymphocytes, monocytes, eosinophils, and basophils.

Serum Biochemistry

Biochemistry lab tests will be collected from the medical records at baseline and every other day through treatment and hospital stay (as applicable) unless an abnormal value is observed. In the case of an abnormal lab result, continue to collect and test those samples to follow subject through resolution.

The following biochemistry lab tests are tested: sodium, potassium, chloride, bicarbonate, urea, creatinine, glucose, total calcium, phosphate, ferritin, high-sensitivity C-reactive protein (hs-CRP), protein, albumin, globulins, total bilirubin, alkaline phosphatase (ALP), alanine aminotransferase (ALT), aspartate aminotransferase (AST) and lactate dehydrogenase (LDH).

Cytokine and Chemokine Assays

Cytokine and chemokine assay lab test results will be collected and recorded before and after treatment (at baseline and again at Day 5 and at hospital discharge). A cytokine panel is tested to include, but not limited to: Tumor Necrosis Factor alpha (TNF α), interferon gamma (IFN γ), Interleukin 1 beta (IL-1 β), interleukins (IL-6, IL-8, IL-10, IL-12). Data is reported for research purposes, and the sample is destroyed after data is collected.

Ordinal Scale for Clinical Improvement

The clinical status will be recorded at every visit from baseline to Day 60 using the World Health Organization (WHO) “Ordinal Scale for Clinical Improvement”. This 8-point ordinal

scale was created to be responsive to the eligible patient population, intervention, and course of illness of COVID-19. The following is scores are collected:

Score	Descriptor
0	No clinical or virological evidence of infection
1	No limitation of activities
2	Limitation of activities
3	Hospitalized, no oxygen
4	Hospitalized, oxygen by mask or nasal prongs
5	Hospitalized, non-invasive ventilation or high-flow oxygen
6	Hospitalized, mechanical ventilation
7	Hospitalized, ventilation + additional organ support – pressors, RRT, ECMO
8	Death

NEWS2 Score for Determining the Degree of Illness

The NEWS2 will be calculated using the oxygenation requirement (room air or supplemental oxygen), SpO2 level, and vitals (body temperature, respiratory rate, heart rate and blood pressure) collected during study visits. The NEWS2 score is recommended by the National Institute for Health and Care Excellence (“NICE”) for managing COVID-19 patients.

Adverse Events

Any documented adverse event. These include but are not limited to the following: cardiac injury, arrhythmia, septic shock, liver dysfunction, acute kidney injury, and multi-organ failure.

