1.2 Schedule of Assessments (SoA)

Visits will be conducted as described:

	Screen	Treatment					Hospitalization/ Continued Care	Follow-Up		
Study Day	-3 to 0	0	1	2	3	4	5	Every day until Day 7	28	60
Visit Window (± days)	--	--	--	--	--	--	--	--	3	3
COVID-19 diagnosis	X									
Informed consent	X									
Medical history and pre-existing conditions	X									
Inclusion/exclusion criteria	X	X								
Urine pregnancy test ¹		X								
Demographics		X								
Randomization		X								
IV treatment			X	X	X	X	X			
Vital signs		X	X	X	X	X	X	X		
Blood oxygen saturation		X	X	X	X	X	X	X		
ECG monitoring (telemetry) ²		X	X	X	X	X	X	X ²		
Hematology ³		X		X		X	X	X ³		
Biochemistry ²		X		X		X	X	X ³		
Cytokine/chemokine assay ⁴		X				X		X ⁴		
Mortality								X	X	X
Ordinal scale for clinical status		X	X	X	X	X	X	X	X	X
NEWS2 score for clinical status		X	X	X	X	X	X	X	X	X
Hospital LOS and ICU LOS			X	X	X	X	X	X	X	X
Date of intubation/ extubation, days on ventilation			X	X	X	X	X	X	X	X
Concomitant medications		X	X	X	X	X	X	X	X	X
Adverse events		X	X	X	X	X	X	X	X	X

¹ As applicable

² Telemetry monitored as needed for patients who have events or abnormal readings requiring measurements.

³ Hematology and biochemistry tests are performed at baseline and every other day through treatment and inpatient stay unless an abnormal value is observed. In the case of an abnormal lab result, continue to collect and test those samples to follow subject through resolution.

⁴ Cytokine and chemokine assays are collected at baseline before treatment, at Day 5 after treatment, and at discharge.

TABLE OF CONTENTS

1	PROTOCOL SUMMARY	3
1.1	Protocol Synopsis.....	3
1.2	Schedule of Assessments (SoA)	9
2	INTRODUCTION	14
2.1	Study Drug	14
2.2	Background to the Disease.....	14
2.3	Previous Human Experience.....	15
2.4	Study Rationale.....	16
2.4.1	Study Background.....	16
2.4.2	Preclinical Data.....	16
2.4.3	Dosing Rationale.....	17
2.5	Benefit and Risk Assessment.....	18
3	STUDY DESIGN.....	19
3.1	Study Design Overview	19
3.2	Study Objectives	20
3.2.1	Primary Objective	20
3.2.2	Secondary Objectives.....	20
3.3	Study Endpoints.....	20
3.3.1	Primary Endpoint	20
3.3.2	Secondary Endpoints	20
3.4	Blinding and Randomization	21
3.5	Data Safety Monitoring Board.....	21
3.6	Stopping rules	21
4	SELECTION OF PARTICIPANTS	22
4.1	Number of Participants	22
4.2	Recruitment Methods.....	22
4.3	Participant Characteristics	22
4.4	Inclusion Criteria	23
4.5	Exclusion Criteria	23

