9.4.2 Secondary Endpoints

Secondary efficacy endpoints assess the effect of IV Ampion compared to SOC on the clinical outcomes for participants with COVID-19 on supplemental oxygen. The secondary endpoints will be tested in a hierarchical manner in the order presented, and thus no adjustment to the alpha level is necessary:

Objective	Endpoint
Secondary Endpoints	
Assess the effect of Ampion compared to placebo on safety	
Incidence of adverse events (AEs) and serious adverse events (SAEs) from baseline to Day 60.
Assess the effect of Ampion compared to placebo on clinical improvement	
Change in ordinal scale from baseline through Day 7.Change in ordinal scale from baseline to hospital discharge or day 14 (whichever occurs first).Change in ordinal scale from baseline to hospital discharge or day 28 (whichever occurs first).Change in NEWS2 score from baseline through Day 5.Change in NEWS2 score from baseline to hospital discharge.Modulation of cytokine levels from baseline to Day 5.
Assess the effect of Ampion compared to placebo on duration of respiratory failure to ventilator-free days.	
Percentage of participants who progress to respiratory failure (i.e., need for mechanical ventilation, ECMO, non-invasive ventilation) by Day 28.

Objective	Endpoint
Assess the effect of Ampion compared to placebo on intensive care	
Percentage of participants who require Intensive Care Unit (ICU) admission by Day 28.ICU-free days through Day 28.ICU LOS from ICU admission to discharge.
Assess the effect of Ampion compared to placebo on hospital stay	
Hospital length of stay (LOS) from admission to discharge.Hospital-free days through Day 28.
Assess the effect of Ampion compared to placebo on oxygen use	
Duration of oxygen use, blood oxygen saturation, and oxygen flow rate from baseline through Day 5.

The efficacy endpoints will be evaluated to estimate the treatment effect and use descriptive statistics including mean, standard deviation, percentages, minimum/maximum, and 95% confidence intervals. All endpoints will be tabulated and presented by treatment arm, cohort (severe and critical), and timepoint. Where appropriate, data will be tabulated and presented cumulatively across cohorts and/or timepoints.

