Where Median_A and Median_S are the median hospital length of stay for the Ampion and placebo groups. Assuming there is no censoring, this will be tested using the Wilcoxon rank sum test via PROC NPAR1WAY. If censoring occurs, e.g., death, then the log rank test will be used based on PROC LIFETEST.

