For any variable, unless otherwise defined, baseline is the last assessment taken prior to the first study drug administration.

4.6 Change from Baseline:

The arithmetic difference between a post-baseline value and the baseline value:

Change from Baseline = (Post-baseline Value – Baseline Value)

Percentage Change from Baseline = [(Post-baseline Value – Baseline Value) / Baseline Value] x 100

4.7 End of Study:

End of study is at Day 60 unless terminated early.

4.8 Enrollment Date:

Enrollment date is the same as the randomization date and is designated Day 0.

4.9 Study Drug:

Study drug in this study is Ampion plus SOC or Placebo plus SOC.

4.10 Randomization Date:

Randomization date is the day the subject is assigned a randomization number on study Day 0.

4.11 Study Day 1:

Day 1 is defined as the first day that study drug is administered to the subject.

4.12 Study Day:

Day of treatment: study day = (visit date - date of Study Day 1 + 1)

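### Hospital length of stay is counted from admission, so the tested endpoint includes pre-randomisation days that treatment cannot affect; the cost is precision and interpretability, not bias

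*Protocol*

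**What the plan says.** Protocol 5.2 (Length of Stay) defines the measure: "Hospital LOS: is defined (in days) as the date of hospital discharge minus date of hospital admission + 1". The endpoint tables in Protocol 1.1, 3.3.2 and 9.4.2 agree with it, listing "Hospital length of stay (LOS) from admission to discharge". In SAP 3.2.6 the two quantities compared "are the median hospital length of stay for the Ampion and placebo groups", and no other time origin is given.

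On timing, SAP 4.8 states: "Enrollment date is the same as the randomization date and is designated Day 0". Protocol 5.1.1 allows screening from Day -3 to Day 0, and Protocol 5.1.3 says: "Begin treatment within 6 hours of randomization". The inclusion and exclusion criteria (Protocol 4.4 and 4.5) set no limit on days already spent in hospital.

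On the test, SAP 3.2.6 says: "Assuming there is no censoring, this will be tested using the Wilcoxon rank sum test via PROC NPAR1WAY". If there is censoring, with death as the example, it switches to the log-rank test. It does not mention delayed entry. Protocol 9.4.2 names a two-sample t-test instead; that conflict is a separate matter.

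**The concern.** The stated objective is the effect of treatment on hospital stay. A day in hospital before randomisation cannot be part of that effect, yet it is added to each patient's outcome. The screening window does not bound the addition, because it limits screening and not prior stay. The critical stratum admits patients who are already ventilated, so the text does not confine entry to the first days of an admission.

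Three things follow. First, if prior stay varies between patients and is unrelated to later stay, it adds variance and lowers power. Second, a patient had to remain in hospital to be randomised. Under the log-rank test with an admission origin, every patient therefore carries a stretch of time in which discharge could not be a study event. Third, the reported medians and the survival curve planned as SAP Figure 9 describe total stay in patients who stayed long enough to be enrolled, not the stay that follows treatment.

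**Working it through.** **The plan's own figure.** The only power figure in the documents is 81.3% for the primary endpoint (8% v 22%, 100 per arm, two-sided 5%, unpooled z-test, binomial enumeration). Exact enumeration gives 81.28%, so it reproduces. It says nothing about hospital stay, for which the plan gives no power, standard deviation (SD) or expected difference. Everything below rests on stated assumptions, with 100 per arm and a two-sided 5% level.

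**Step 1: added variance, t-test.** Assume prior days are independent of later stay, so

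SD_total = √(SD_post² + SD_pre²), and power = Φ(δ / (SD_total × √(2/n)) − 1.960).

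Take SD_post = 7 days (assumed) and the δ that has 80% power when counted from randomisation: δ = 7 × √(2/100) × (1.960 + 0.842) = 2.77 days. For prior days uniform on 0, 1, 2, 3, the variance is (4² − 1)/12 = 1.25, so SD_pre is about 1.1. As a worked case with SD_pre = 3: SD_total = √(49 + 9) = 7.62, the standardised difference is 2.575, and Φ(2.575 − 1.960) = Φ(0.615) = 73.1%.

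| SD of prior days | Power | n per arm for 80% |
|---|---|---|
| 0 | 80.0% | 100 |
| 1.1 (uniform 0–3) | 79.0% | 103 |
| 2 | 76.8% | 109 |
| 3 | 73.1% | 119 |
| 5 | 62.5% | 152 |

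The result depends on SD_post. With SD_pre = 3 and δ reset to give 80% from randomisation, power is 67.1% if SD_post = 5 and 76.5% if SD_post = 10.

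**Step 2: all three named tests, by simulation.** Assumptions: Weibull discharge times (shape 1.3) with a control median of 8 days; discharge hazard ratio 1.55; in-hospital deaths censored, at 0.012 per day; follow-up capped at 60 days; t-test and Wilcoxon on discharged patients; whole prior days uniform and independent of later stay. There were 2,000 trials per power figure, with both clocks applied to the same trials.

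| Prior days | Clock | Log-rank | Wilcoxon | t-test |
|---|---|---|---|---|
| 0–3 | randomisation | 84.0% | 66.2% | 77.7% |
| 0–3 | admission | 83.2% | 63.7% | 76.3% |
| 0–7 | randomisation | 81.7% | 64.0% | 75.6% |
| 0–7 | admission | 78.5% | 59.0% | 70.7% |
| 0–14 | randomisation | 82.8% | 66.7% | 77.6% |
| 0–14 | admission | 69.6% | 49.4% | 60.2% |

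The loss is 0.8 to 2.5 points for 0–3 days, 3.2 to 5.0 points for 0–7 days, and 13.2 to 17.4 points for 0–14 days.

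**Step 3: type I error.** With no treatment effect (3,000 trials), rejection rates ran from 4.5% to 5.8% across both clocks and all tests, with simulation error of about 0.4 points. Neither clock inflates it.

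**Step 4: a second model.** Lognormal later stay (medians 8 v 6 days, log-SD 0.7), no deaths, Wilcoxon test, exponential prior stay. Power is about 80% from randomisation and about 77%, 68% and 56% from admission, for mean prior stays of 1, 3 and 5 days. Repeat runs agreed within about 2 points. With prior stay uniform on 0–3 days, this model loses about 2 to 3 points.

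**The case against.** The strongest reply is that the effect is small and falls on an endpoint of little weight. This largely stands. The 3-day screening window is the only related figure in the documents; if it roughly describes prior stay, the loss is 1 to 3 points. Double-digit losses need a wide spread, such as 0–14 days or an exponential with mean 3 to 5 days, and nothing in the documents shows that spread. The larger Wilcoxon losses also assume no deaths. The primary endpoint includes death, so some censoring is likely and the log-rank test may well be the one used; there the loss is about 1 to 3 points for 0–3 to 0–7 days. Prior days that were the same for everyone would add no noise to a t-test or Wilcoxon test, and a strong negative correlation with later stay would also weaken the noise argument.

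Protocol 9.4.2 also lists hospital-free days through Day 28, which suggests a window running from study entry. It is not defined there and does not appear in the SAP, so it does not repair this endpoint.

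Three stronger readings are tempting, and the documents support none of them:

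- A reader might infer a biased comparison from the event-free time. That time arises in both arms and randomisation balances it on average; type I error was unaffected.
- A reader might infer that a chance imbalance in prior days would pass for a treatment effect. The test's alpha already allows for that.
- A reader might infer that hospital stay is the only SAP hypothesis not timed from randomisation. It is not: the median ICU stay hypothesis in SAP 3.2.4 has no such wording either, and Protocol 5.2 starts ICU stay at the first study date in ICU.

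**Conclusion.** The point holds as a matter of precision and interpretability. The text counts hospital stay from admission, sets no limit on prior stay, and specifies no delayed entry for the log-rank version; no other section corrects this. Assuming prior days are independent of later stay, the cost is about 1 to 3 points of power if patients are randomised within about 3 days of admission, and roughly 10 points or more only if prior stay varies widely. The variance and interval needed to choose within that range are not in the documents.

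The consequence for the trial is minor. Hospital stay is item 3.2.6, the last in the order that SAP 8.6 uses for hierarchical testing, so it is formally tested only if everything before it succeeds. The case for changing it is that the revised endpoint would measure the stated objective at little cost.

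**What to change.** In Protocol 5.2, 3.3.2 and 9.4.2, in SAP 3.2.6 and for SAP Figure 9, define the tested hospital stay as discharge date minus randomisation date + 1, and align the synopsis in Protocol 1.1. Summarise days from admission to randomisation by arm as a baseline characteristic. Keep admission-to-discharge stay as a descriptive summary.

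Admission, discharge and randomisation dates are already recorded, so there is no new data collection and no added patient contact. The cost is a short wording amendment, which under Protocol 10.3 needs approval by the sponsor, the IRB/IEC and the health authorities, and a matching SAP revision. The handling of deaths and the t-test versus Wilcoxon/log-rank conflict need their own resolution; this change does not settle them.

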3.3.2 Secondary Endpoints

Secondary efficacy endpoints assess the effect of IV Ampion compared to SOC on the clinical outcomes for participants with COVID-19 who require supplemental oxygen as follows:

Objective	Endpoint
Secondary Endpoints	
Assess the effect of Ampion compared to placebo on safety	
Incidence of adverse events (AEs) and serious adverse events (SAEs) from baseline to Day 60.
Assess the effect of Ampion compared to placebo on hospital stay	
Hospital length of stay (LOS) from admission to discharge.
Assess the effect of Ampion compared to placebo on oxygen use	
Duration of oxygen use, blood oxygen saturation, and oxygen flow rate from baseline through Day 5.
Assess the effect of Ampion compared to placebo on duration of respiratory failure to ventilator-free days	
Percentage of participants who progress to respiratory failure (i.e., need for mechanical ventilation, ECMO, non-invasive ventilation) by Day 28.
Assess the effect of Ampion compared to placebo on intensive care	
Percentage of participants who require Intensive Care Unit (ICU) admission by Day 28.ICU-free days through Day 28.ICU LOS from ICU admission to discharge.
Assess the effect of Ampion compared to placebo on clinical improvement	
Change in ordinal scale from baseline through Day 7.Change in ordinal scale from baseline to hospital discharge or Day 14 (whichever occurs first).

Objective	Endpoint
	
Change in ordinal scale from baseline to hospital discharge or Day 28 (whichever occurs first).
Assess the effect of Ampion compared to placebo on clinical health	
Change in NEWS2 score from baseline through Day 5.Change in NEWS2 score from baseline to hospital discharge.
Assess the effect of Ampion compared to placebo on oxygen use	
Duration of oxygen use, blood oxygen saturation, and oxygen flow rate from baseline through Day 5.

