3.2 Secondary Endpoints

3.2.1 Change in ordinal scale from baseline through Day 7, Day 14 and Day 28.

The hypotheses to be tested are:

$$H_0: \mu_A = \mu_S \text{ versus } H_A: \mu_A \neq \mu_S$$

Where μ_A and μ_S represent the ordinal scale shift through day 7, 14, and 28 for Ampion and Placebo after randomization. The difference between Ampion and Placebo with respect to the change from baseline at day 7, 14, and 28 will be tested utilizing a Wilcoxon rank-sum test via PROC NPAR1WAY. To assess any potential time trends, an exploratory repeated measures analysis of variance will be performed with terms for treatment, time and the interaction between the two. This will be done utilizing PROC GLM with the REPEATED option.

3.2.2 Change in NEWS2 score from baseline through Day 7, or discharge if earlier.

The hypotheses to be tested are:

$$H_0: \mu_A = \mu_S \text{ versus } H_A: \mu_A \neq \mu_S$$

Where μ_A and μ_S represent the mean change from baseline in the NEWS2 score assessment through day 7 for Ampion and Placebo after randomization. The difference between Ampion and Placebo with respect to the change from baseline at day 7, or discharge if earlier, will be tested utilizing a Wilcoxon rank-sum test via PROC NPAR1WAY. To assess any potential time trends an exploratory repeated measures analysis of variance will be performed with terms for treatment, time and the interaction between the two. This will be done utilizing PROC GLM with the REPEATED option.

3.2.3 Percentage of participants who progress to respiratory failure by Day 28.

The hypotheses to be tested are:

$$H_0: \pi_A = \pi_S \text{ versus } H_A: \pi_A \neq \pi_S$$

Statistical Analysis Plan (SAP) for Clinical Study AP-017

Let π_A and π_S represent the percentage of patients who have respiratory failure for Ampion and control during the first 28 days after randomization.

This difference will be tested utilizing the appropriate chi-square test or Fisher's exact test utilizing PROC FREQ with the EXACT option, if needed.

Also, the median time to respiratory failure will be tested for difference between the two groups via the log-rank test. The log-rank test will be performed using PROC LIFETEST; and the estimation of the time-to-event distributions will be performed using the method of Kaplan and Meier.

3.2.4 Percentage of participants who require Intensive Care Unit (ICU) admission by Day 28; ICU-free days through Day 28; ICU length of stay (LOS) from ICU admission to discharge.

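### Respiratory failure by Day 28 has two conflicting definitions, and after Day 7 the schedules date only its intubation component

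*Protocol*

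**What the plan says.** **Definition.** Protocol 3.3.2 gives the endpoint as "Percentage of participants who progress to respiratory failure (i.e., need for mechanical ventilation, ECMO, non-invasive ventilation) by Day 28". The synopsis and 9.4.2 use the same three components. Protocol 5.2, under Intubation/Extubation, gives four: "Proportion of participants who progress to respiratory failure (i.e., need for mechanical ventilation, ECMO, non-invasive ventilation, or high-flow nasal cannula oxygen) will be evaluated". SAP 3.2.3 names the endpoint without listing components.

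**Analysis.** SAP 3.2.3 compares the Day 28 percentages by chi-square or Fisher's exact test and adds a time-to-event analysis: "Also, the median time to respiratory failure will be tested for difference between the two groups via the log-rank test", with Kaplan-Meier curves. SAP 8.6 tests the secondary endpoints hierarchically in the order of Section 3.2, where this one stands third.

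**Collection.** The only respiratory-support row with dates in either schedule is "Date of intubation/ extubation, days on ventilation". Protocol 5.2 says of it: "Date and time of intubation/extubation and days on ventilator will be recorded at hospital discharge, Days 28 and 60, as applicable". Oxygen use (saturation and flow rate), again in 5.2, "will be recorded at every visit from baseline to Day 5". Oxygen mode is in the 5.1.4 inpatient list, under the heading "Hospitalization Period, as applicable (Day 6 through Day 7)". The text below that heading applies the list until the inpatient stay ends, and the table of contents also runs the section to discharge. The schedule stops daily recording at Day 7. Protocol 5.1.5 (Days 28 and 60) includes the ordinal scale but no dates of respiratory support.

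**The concern.** An incidence endpoint with a log-rank test needs two things for each component: a rule for what counts as an event, and a recorded onset date.

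The rule is in conflict. A patient who steps up to high-flow oxygen and no further is an event under Protocol 5.2 and a non-event under the endpoint tables. The SAP does not choose, so two analysts could report different counts from the same data.

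The onset date is scheduled for intubation only. For the other components the follow-up from Day 8 to Day 28 rests on one or two status readings. Because the endpoint sits third in the hierarchy, an under-counted or ambiguous result there also decides whether ICU admission, cytokines and hospital stay can be formally tested.

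**Working it through.** **1. The plan's own figure.** There is none for this endpoint. The only stated power, 81.3%, belongs to the primary endpoint (8% versus 22%, 100 per arm, two-sided 5%, unpooled z-test). Exact binomial enumeration gives 81.28%, so it reproduces. It serves below only as a scale.

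**2. The definitions side by side.**

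| Source | Invasive ventilation | ECMO | Non-invasive ventilation | High-flow oxygen |
|---|---|---|---|---|
| Synopsis, 3.3.2, 9.4.2 | yes | yes | yes | no |
| Protocol 5.2 | yes | yes | yes | yes |
| SAP 3.2.3 | not stated | not stated | not stated | not stated |

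The difference bears on a randomisation stratum. Inclusion criterion 3b admits critical patients on high-flow oxygen, non-invasive ventilation or endotracheal ventilation. Under 5.2 all of them meet the definition at baseline. Under the endpoint tables those on high-flow oxygen are still at risk. Neither document says how progression is counted for a patient who already qualifies.

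**3. What the schedules hold from Day 8 to Day 28.**

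| Component | Scheduled onset date | Status reading (ordinal scale) |
|---|---|---|
| Invasive ventilation | intubation date | scores 6 and 7 |
| Non-invasive ventilation | none | score 5, shared with high-flow oxygen |
| High-flow oxygen | none | score 5, shared with non-invasive ventilation |
| ECMO | none of its own | score 7, shared with other organ support |

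Score 7 places ECMO on top of ventilation, so an ECMO patient graded there would normally have an intubation date too. The practical gap is therefore non-invasive ventilation and, under 5.2, high-flow oxygen. Under the three-component definition, score 5 cannot separate an event from a non-event.

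The SAP outputs do not fill the gap. Table 10.2.4 is to show progression over time, but Listing 15 holds ventilation days, ventilation-free days and extubation date, and Listing 12 names no data source.

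**4. What the status readings can see.** Assume one episode of *d* days, onset uniform over the 21 days from Day 8 to Day 28, and visits exactly on Days 14 and 28.

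- Day 28 only (protocol schedule): share under way on the visit day = d/21.
- Days 14 and 28 (SAP schedule), for d up to 14: share = (min(d, 7) + d)/21, because only onsets on Days 8 to 14 can be seen on Day 14.

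| Episode length | Day 28 only | Days 14 and 28 |
|---|---|---|
| 3 days | 3/21 = 14% | 6/21 = 29% |
| 5 days | 5/21 = 24% | 10/21 = 48% |
| 7 days | 7/21 = 33% | 14/21 = 67% |
| 10 days | 10/21 = 48% | 17/21 = 81% |

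Later episodes are thus partly seen, but a status reading never supplies a start date.

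**5. A scale for lost events.** Suppose, purely as an assumption, that 22% and 8% stood in for respiratory failure and the same share of events were missed in both arms. A 10% loss shrinks the difference from 14 to 12.6 points (0.9 × 14). By the same enumeration, power falls from 81% to 76% with 10% missed, 71% with 20% and 64% with 30%. The documents do not say which loss, if any, would apply.

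**The case against.** The strongest reply is that the plan records more than intubation dates. The text of 5.1.4 and its contents entry can be read as keeping oxygen mode and the ordinal scale going until discharge, which would supply dates for inpatients. The ordinal scale is read again at Day 28, and at Day 14 in the SAP schedule. ICU dates, concomitant therapies and adverse events continue after Day 7. An escalation reported as a serious adverse event carries an onset date and time under Protocol 8.4.1. The named comparison is of percentages, with the log-rank test as an addition.

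Much of this stands. A reader might infer that only intubation dates are scheduled after Day 7 and that later events go unseen. The documents do not support that. A patient on non-invasive ventilation from Day 10 to Day 15 would score 5 on Day 14 under the SAP schedule, although the protocol schedule, with Day 28 only, could miss the episode. A reader might also describe the late curve as intubations and deaths, but death is not a component in any version of the endpoint.

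The reply does not close the gap. The heading of 5.1.4 and the schedule stop at Day 7, and a site working from the schedule would stop there. Neither document names adverse events, ICU dates or therapies as a source for this endpoint. The percentage also depends on the definition and on complete capture, so it is affected whether or not the log-rank test matters.

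**Conclusion.** The point holds in two parts. First, the definitions conflict on high-flow oxygen, and the SAP does not resolve the conflict; this follows from the text alone. Second, after Day 7 neither schedule contains a dated record of non-invasive ventilation, high-flow oxygen or ECMO. If sites follow the schedule, non-intubation events on Days 8 to 28 are partly missed and lack a scheduled onset date. The Day 28 percentage may then be too low, and the Kaplan-Meier and log-rank analyses lack event times. If sites instead follow the text of 5.1.4, the gap narrows for inpatients, which is why that contradiction must be settled.

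The size cannot be estimated from the documents. A reader might put it at 7.5% to 15% of events by supposing that 15% to 30% start after Day 7 and half of those never reach intubation (15% × 0.5 to 30% × 0.5). Those inputs are not in the documents, and the product gives no credit to the ordinal scores. The shares and power figures in the working are likewise illustrations under stated assumptions.

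**What to change.** 1. In both schedules and in Protocol 5.1.4, 5.1.5 and 5.2, record start and stop dates of invasive ventilation, non-invasive ventilation, high-flow oxygen and ECMO from randomisation to Day 28. Take them from the chart while the patient is in hospital, and at the existing Day 28 contact otherwise.
2. Reconcile the end of the 5.1.4 period across its heading, its text, the table of contents and the schedule.
3. Use one endpoint definition in the synopsis, 3.3.2, 5.2, 9.4.2 and SAP 3.2.3. One option is the three-component version already in the endpoint tables, with the high-flow version as a sensitivity analysis.
4. In SAP 3.2.3, name the data source and event date for each component, and state how progression is counted for critical patients already on a qualifying support mode at baseline.

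The cost is a few eCRF date fields, matching wording and a small amount of extra abstraction. No visit or procedure is added. Dates not collected during the trial may be hard to recover afterwards.
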